5.5 Study Data – Statistical Analysis

- Sample Size:

This study is designed to compare fused ¹¹C-choline PET/CT and MRI scans against a standard CT scan and MRI scan. Based on the literature, the group detection rates are approximately 50%. In this study a 20 percentage point increase (eg: from 15 – 35 percent) in detection rate is the desired goal. The study is a paired design, in that each procedure will be performed on each individual. The important performance characteristics of these tests, including sensitivity, specificity, positive predictive value, and negative predictive value will be examined within this study. A sample size estimate was derived using a p-value of 0.05, a power of 80 %, and a paired chi square test for proportions. It was further assumed that the false positive rate is about 4 % and the false negative rate is about 20 %, which are similar to the literature. This would indicate approximately 66 pairs of data. To compare, an independent chi square test would indicate about 71 subjects per group for a comparable 20 point change. Increasing the sample size by 10 percent, for attrition, would increase the number of paired samples to about 73. Increasing the number of pairs to 100 will provide some flexibility on the false positive and false negative rates.

While more than 100 patients may be admitted into the study under expanded access, for the purposes of the comparison study and resulting data analysis, only the first 100 qualified patients will be admitted into the study and included in the study data.

- Data Analysis:

1. True positives will consist of evidence of metastatic prostate cancer on conventional CT or MRI images or on ¹¹C-choline PET/CT or MRI images confirmed with biopsy, surgical

pathology, or by response to treatment with androgen suppression or other medical or radiation therapy.

2. True negatives will consist of negative images.
3. False positive will consist of evidence of metastatic prostate cancer on conventional CT or MRI images or on ^{11}C -choline PET/CT or MRI images, but without corresponding confirmation from biopsy, surgical pathology or response to treatment.
4. False negative will consist of negative images, but with positive biopsy, surgical pathology or a response to treatment.
5. Sensitivity, specificity, PPV, and NPV of CT and MRI and of ^{11}C -choline PET/CT and MRI will be calculated
6. Performance characteristics between ^{11}C -choline PET/CT and PET/MRI will be compared.
7. The optimal PSA trigger value in ^{11}C -choline PET/CT and PET/MRI positive patients will be calculated.
8. Demographic, clinical, and pathologic factors that predict a positive ^{11}C -choline PET/CT or PET/MRI will be determined through a multivariable analysis.

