5. Patients entered into the study will undergo a ^{11}C -choline PET CT scan and MRI scan. The CT scan will be performed with intravenous contrast unless deemed unsafe by lab values. The CT and MRI images will be evaluated for evidence of metastatic prostate cancer. The ^{11}C -choline PET CT and MRI images will be evaluated for evidence of metastatic prostate cancer. Unequivocal evidence of metastasis on both conventional imaging and ^{11}C -choline PET will be considered a true positive. Evidence of metastasis on conventional imaging or ^{11}C -choline PET will be confirmed with biopsy or surgical pathology when possible, or by response to treatment on subsequent imaging. If confirmation of metastasis is not achievable by biopsy or surgical pathology, then confirmation will be achieved with ^{11}C -choline PET CT and MRI images obtained 3 months after treatment conclusion. Rates of confirmed metastasis between conventional CT and MRI images will be compared with the ^{11}C -choline PET CT and MRI images.
6. Upon conclusion of each imaging protocol, the referring physician will receive written documentation of the results. At this time, the patient will be considered off study and no further follow up is required.

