6.2 Warnings and Precautions

- Imaging errors have been reported during previous clinical studies with ^{11}C -choline PET and PET/CT imaging. A negative image does not rule out the presence of recurrent prostate cancer and a positive image does not confirm the presence of recurrent cancer. ^{11}C -choline uptake is not specific

Investigatory New Drug
**Clinical Trial Protocol:
Choline C11 Injection**

Revision Date: _01/30/2015

Page 20 of 59

for prostate cancer and may occur with other types of cancer, such as lung carcinoma and brain tumors.

- Blood PSA levels < 2 ng/mL have been associated with poor performance ^{11}C -choline PET imaging, with indications of higher numbers of false positive and false negative results.
- Tissue inflammation as well as prostatic hyperplasia have been associated with false positive ^{11}C -choline PET images.
- Concomitant colchicine or androgen-deprivation therapeutic drugs, such as luteinizing hormone-releasing analogs and anti-androgen drugs, may interfere with ^{11}C -choline PET imaging. One published report of ^{18}F methylcholine PET imaging indicated that discontinuation of colchicine for two weeks resolved the colchicine effect. The impact of discontinuation of androgen-deprivations therapy upon ^{11}C -choline PET imaging has not been established.

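### Section 5.5 confirms a lesion without pathology only by treatment response, so one that progresses is scored a false positive and nothing can be indeterminate

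*Combined protocol and SAP*

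**What the plan says.** All references are to the comparison protocol; the expanded-access protocol in the same file plans no accuracy analysis.

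- **5.5, item 1 (true positive):** a positive image confirmed by biopsy, surgical pathology, "or by response to treatment with androgen suppression or other medical or radiation therapy".
- **5.5, item 3 (false positive):** a positive image "but without corresponding confirmation from biopsy, surgical pathology or response to treatment".
- **5.5, item 4:** "False negative will consist of negative images, but with positive biopsy, surgical pathology or a response to treatment".
- **5.1, step 5:** a lesion is confirmed by biopsy or surgical pathology "when possible, or by response to treatment on subsequent imaging". Where pathology is not achievable, confirmation uses choline PET CT and MRI "images obtained 3 months after treatment conclusion". The same step has a concordance rule: "Unequivocal evidence of metastasis on both conventional imaging and" choline PET is a true positive.
- **5.1, step 6:** once the imaging report is sent, "the patient will be considered off study and no further follow up is required".
- **5.4.1, item 10:** the readings are compared with histology or with imaging after treatment.
- **6.2:** "Concomitant colchicine or androgen-deprivation therapeutic drugs, such as luteinizing hormone-releasing analogs and anti-androgen drugs, may interfere with" choline PET, and the effect of stopping androgen deprivation is not established. Inflammation and prostatic hyperplasia are named as causes of false-positive uptake.

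**The concern.** Items 1 and 3 split all positives into two classes, and response is the only route to the first class for a lesion without pathology. A bone or nodal lesion that enlarges between the study scan and follow-up is evidence for cancer. It has not responded, however, so item 3 counts it as an error of the scan. A lesion that nobody could re-image is counted the same way.

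Item 4 does not say what must respond or how this is measured. Read literally, response of purely local disease would turn a negative scan into a false negative for metastasis.

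A smaller concern runs the other way. Loss of choline uptake after androgen deprivation may be a drug effect, so taken alone it is not specific evidence that the lesion was metastatic.

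These items define the cells behind objectives B and E and the results that 5.6 intends to publish. 5.1 compares rates of confirmed metastasis between conventional and choline PET images. A PET-only lesion that loses confirmation therefore drops out of exactly the discordant results on which a paired comparison depends.

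**Working it through.** **The plan's own figures.** No figure in the plan quantifies this point. The computable figures in 5.5 are the sample sizes, and they reproduce. With discordant cells b = 0.20 and c = 0.04, n = (1.960 + 0.842)² × [(b + c) − (b − c)²] / (b − c)² = 65.7, so 66 pairs. The 71 per group follows from the arcsine formula for 15% versus 35% (70.9), and 66 × 1.10 gives 73. None of this bears on whether the scoring rule is sound.

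**The rules applied to each type of lesion without pathology:**

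| Course at follow-up | 5.5 items 1 and 3 | 5.1 step 5 |
|---|---|---|
| Regresses | True positive | True positive |
| Progresses, unequivocal on both conventional imaging and PET | False positive | True positive (concordance rule) |
| Progresses, PET-only or equivocal on one | False positive | Not confirmed |
| No follow-up images | False positive | Not confirmed, unless concordant |

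Row 2 is a direct conflict between sections. Row 3 is misclassified under either reading.

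**Illustration 1: PPV.** Assume 35 PET-positive men with a true PPV of 80%, so 28 true and 7 false. Let f be the share with pathology, r the probability that a real lesion without pathology responds, and q the probability that a false one appears to respond.

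Scored TP = 28 × [f + (1 − f) × r] + 7 × (1 − f) × q

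The value f = 0.414 is the pathology share for true positives in the retrospective review cited in 1.2.1; applying it to all positives is an assumption. The documents give no value for r or q. The ranges assumed are 10% to 40% non-response (r = 0.9 to 0.6) and q = 0.4 to 0.8, the latter being 50% to 100% of false lesions in men given systemic therapy, times 80% appearing to respond.

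| r | q | Scored TP | Reported PPV |
|---|---|---|---|
| 0.9 | 0 | 28 − 28 × 0.586 × 0.10 = 26.36 | 75% |
| 0.6 | 0 | 28 − 28 × 0.586 × 0.40 = 21.44 | 61% |
| 1 | 0.4 | 28 + 7 × 0.586 × 0.40 = 29.64 | 85% |
| 1 | 0.8 | 28 + 7 × 0.586 × 0.80 = 31.28 | 89% |
| 0.9 | 0.4 | 28 − 1.64 + 1.64 = 28.00 | 80% |
| 0.6 | 0.8 | 28 − 6.56 + 3.28 = 24.72 | 71% |

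**Illustration 2: specificity and sensitivity.** The same review reports sensitivity 93%, specificity 76% and PPV 91%. These imply a prevalence of (0.91 × 0.24) / (0.91 × 0.24 + 0.09 × 0.93) = 0.723. Per 100 men this gives TP 67.2, FN 5.1, FP 6.6 and TN 21.1. With f = 0.414:

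| r | q | Real lesions moved to FP | False lesions moved to TP | Specificity | PPV |
|---|---|---|---|---|---|
| 1 | 0 | 0 | 0 | 0.760 | 0.910 |
| 0.9 | 0 | 3.9 | 0 | 0.665 | 0.857 |
| 0.6 | 0 | 15.8 | 0 | 0.484 | 0.697 |
| 1 | 0.6 | 0 | 2.3 | 0.830 | 0.942 |
| 0.8 | 0.3 | 7.9 | 1.2 | 0.612 | 0.819 |

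Sensitivity stays between 0.910 and 0.932 over these rows. This holds image-negative men as correctly classified, so the effect of item 4 is not included.

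**Paired comparison.** Power = Φ{(b − c)√n / √[(b + c) − (b − c)²] − 1.96}. If 10% or 20% of both discordant cells lose confirmation (an assumption), power falls from 80% to 75% or 70% at 66 pairs, and from 93% to 90% or 86% at 100 pairs.

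**The case against.** The best defence is that 5.1 and 5.4.1 already contain much of what 5.5 lacks. Pathology comes first where possible, lesions unequivocal on both modalities are true positives without any response, and response is read on imaging. This narrows the problem considerably. It does not remove it: the scoring rules in 5.5 repeat neither the concordance rule nor the imaging restriction, and no section accepts progression as confirmation.

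A reader might go further in four ways that the documents do not support.

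- **That a fall in PSA would confirm any lesion.** No section names PSA as the response measure, and 5.1 and 5.4.1 both point to imaging. The fair criticism is that 5.5 should say so.
- **That choline PET simply confirms itself.** The follow-up in 5.1 includes CT and MRI. It is also timed after treatment ends, whereas 6.2 warns about concomitant drugs. What remains is narrower: uptake loss alone is weak evidence, because 6.2 says that the effect of stopping these drugs is not established.
- **That PPV could be reported anywhere from 48% to 96%.** That is the same calculation with f = 0, (28 − 11.2)/35 and (28 + 5.6)/35. It ignores pathology and sets opposite extremes side by side. With both errors acting and f = 0, the result is 80% or 64%.
- **That men enrolled after PSA rises on androgen suppression (4.1.1, item 1d) are the most exposed.** Item 1 accepts other therapies too, and the documents give no response rates for this group.

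**Conclusion.** The point stands in limited form. As written, 5.5 misclassifies a real metastasis without pathology that progresses, has no class for lesions that cannot be assessed, and disagrees with 5.1 on concordant lesions. If the concordance rule applies, the exposure is confined to lesions without pathology that are not unequivocal on both modalities, mainly PET-only ones.

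The two errors push PPV and specificity in opposite directions. The documents do not allow the net bias to be signed, so it could not be corrected afterwards. Under the stated assumptions a true PPV of 80% could be reported as about 61% to 89%. Specificity is also sensitive, while sensitivity changes little. It would therefore be too strong to say that all four accuracy measures merely reflect response to therapy. The defect in the rule is certain from the text; its size rests on assumed response shares and a borrowed pathology share.

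**What to change.** Revise 5.5 items 1, 3 and 4 before any images are scored:

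1. Count a lesion without pathology as confirmed if the same lesion regresses or progresses on the follow-up imaging already described in 5.1. Loss of choline uptake alone after androgen deprivation does not confirm it.
2. In item 4, require pathology or imaging evidence of metastasis at follow-up, not treatment response of any kind.
3. Carry the 5.1 concordance rule and the imaging restriction into 5.5, or otherwise reconcile the two sections.
4. Class a positive with neither pathology nor assessable follow-up imaging as indeterminate. Report results with indeterminates excluded, then with all counted as true, then with all counted as false.
5. Report pathology-confirmed results separately.

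Steps 5 and 6 of 5.1 must also be reconciled. One relies on imaging after treatment and the other ends follow-up at the report, so the images that any version of the rule needs are not secured.

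The cost in 5.5 is wording and a few extra tables; securing the follow-up images is the practical burden. Some men become indeterminate and precision falls slightly. Some error remains: a real lesion that stays unchanged would still be scored false, and a benign lesion that regresses would still be scored true. This is why the pathology-confirmed results should stand on their own. No PSA condition is needed; serial PSA after the scan is not among the data listed in 5.1.

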5.4 Imaging Review and Interpretations

5.4.1 Image Review

There will be two aspects to the evaluation, interpretation and use of the imaging data that is produced as part of this study. First, the information will be used immediately by the primary treatment physician to best assess the patient's status and select a therapy regimen. Second, at the end of the study, all of the patient data will be gathered for a comprehensive review which will proceed as follows:

1. Each patient will be assigned a research participant number at the time of consent.
2. This participant number will be substituted for all patient identifying information, where possible.
3. Any remaining patient identification information will be scrubbed from the patient files.
4. The patient identifier key will be stored on a password protected computer at DMH.
5. Access to this identifier key will be restricted from any of the data reviewers.
6. Scrubbed patient images with the identifier will be saved to a compact disc for radiologist review.
7. Studies will be presented in a random order for analysis.

8. The imaging studies will be interpreted by board certified radiologists:
 - a. Dr. [name]
 - b. Dr. [name]
 - c. Dr. [name]
9. Worksheets will be saved in a locked cabinet at DMH. The worksheets will be scanned and added to the secure computer study database.
10. The imaging reviews will be compared to the histological data or post-treatment imaging data for statistical analysis.

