10.2 Data Handling and Record Keeping

10.2.1 Case Report Forms

Adequate and accurate CRFs should be maintained and all relevant observations and data related to the study should be recorded. This should include patient demographic data such as age, race, and gender; medical history and physical examination; a checklist of inclusion and exclusion criteria; biopsy and/or histology results; clinical assessments from patient medical history; AEs; therapeutic treatments and results; and final interpretation and evaluation of imaging studies completed by the readers. The Monitor will review all CRFs and compare data to that contained in clinic notes and patients' medical records to ensure they match.

The CRF will be signed and dated by the Principal Investigator or designee after his/her review. In addition, source documents will be provided. Each Investigator will be responsible for the timeliness, completeness, and accuracy of the CRFs and will make these forms available for thorough review by the Monitor at each scheduled monitoring visit.

All instances of missing or incorrect data must be given the Investigator's full attention. While it is recognized the certain tests may, on occasion, not be performed either through human error, lack of patient cooperation, or in the interest of good medical practice, these instances should be infrequent. In the event they do become frequent, it is the binding legal responsibility of the Sponsor to consider these a protocol violation and to take appropriate corrective measures.

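### Section 5.5 has no class for unverified patients: a metastasis missed by every scan becomes a true negative, and a positive never confirmed becomes a false positive

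*Combined protocol and SAP*

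**What the plan says.** All references are to the comparison protocol. The expanded-access protocol bound with it plans no such analysis.

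- **Section 5.5, Data Analysis, items 1 to 4.** A true positive is imaging evidence of metastasis that has been confirmed by tissue or by treatment response. For the rest, "True negatives will consist of negative images". A false positive is a positive image lacking that confirmation. A false negative is a negative image accompanied by positive tissue or a treatment response. There is no fifth class.
- **Section 5.1, step 5.** Imaging evidence of metastasis "will be confirmed with biopsy or surgical pathology when possible, or by response to treatment on subsequent imaging". Where tissue cannot be had, the fallback is PET/CT and MRI "images obtained 3 months after treatment conclusion". Separately, "Unequivocal evidence of metastasis on both conventional imaging and ^{11}C -choline PET will be considered a true positive". The comparison is then described as follows: "Rates of confirmed metastasis between conventional CT and MRI images will be compared" with those on PET.
- **Section 5.1, step 6.** Once results go to the referring physician, "At this time, the patient will be considered off study and no further follow up is required".
- **Section 5.4.1, item 10.** "The imaging reviews will be compared to the histological data or post-treatment imaging data for statistical analysis".
- **Section 10.2.1.** The CRF should hold, among other things, "biopsy and/or histology results; clinical assessments from patient medical history; AEs; therapeutic treatments and results".
- **Section 2 (objectives B and E) and section 5.6** promise sensitivity, specificity, PPV and NPV, and comparisons of them between modalities.

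**The concern.** Each of the four measures needs a disease status obtained independently of the scan being judged. Section 5.1 seeks one only for men with a positive image. A man negative on every scan is verified only if routine care happens to produce tissue or treatment data; otherwise he is counted as disease-free. Section 6.2 itself warns that a negative image does not exclude recurrence.

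The positive side has the mirror problem. Item 3 does not separate a finding that was tested and refuted from one that was never tested. Sections 5.1 and 5.5 also disagree about a patient clearly positive on both conventional imaging and PET but never confirmed: he is a true positive under one and a false positive under the other.

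At stake are objective B, the comparisons in objective E, and what section 5.6 says will be published. Sensitivity and NPV are expected to look too good when missed disease is proven less often than detected disease. PPV and specificity look too poor when real positives go unconfirmed.

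**Working it through.** **1. The plan's own figure.** Section 5.5 gives about 66 pairs (p-value 0.05, power 80%, paired chi-square, rates of 4% and 20%). Taking these as the discordant cells, two-sided: n = (1.960 + 0.842)² × (s − d²)/d², with s = 0.20 + 0.04 = 0.24 and d = 0.20 − 0.04 = 0.16. This is 7.849 × 0.2144/0.0256 = 65.7, so 66. The sample size reproduces and is not the fault here.

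**2. Illustrative cells.** Inputs from section 5.5: 100 patients, and example detection rates of 15% and 35%. Assumed: 4 conventional-only positives. The cells are then 11 positive on both, 24 PET-only, 4 conventional-only and 61 neither.

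**3. Negatives (items 2 and 4).** Assume all positives are real and confirmed, and h further metastases lie among the 61, none proven. The 4 conventional-only cases do count as PET false negatives.

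- Reported: sensitivity 35/(35 + 4) = 89.7%; NPV 61/65 = 93.8%.
- True: sensitivity 35/(39 + h); NPV (61 − h)/65.

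| h (assumed) | True sensitivity | True NPV |
|---|---|---|
| 5 | 35/44 = 79.5% | 56/65 = 86.2% |
| 10 | 35/49 = 71.4% | 51/65 = 78.5% |
| 20 | 35/59 = 59.3% | 41/65 = 63.1% |

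The error shrinks as missed cases are proven. With h = 10 and 25%, 50% or 75% proven, reported sensitivity is 35/41.5 = 84.3%, 35/44 = 79.5% or 35/46.5 = 75.3%, and NPV is 58.5/65 = 90.0%, 56/65 = 86.2% or 53.5/65 = 82.3%.

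**4. Other cells.**
- Discordant cells of 20 and 4, as in the 66-pair figure (other cells 11 and 65, assumed): reported 31/35 = 88.6% and 65/69 = 94.2%; true with h = 10, 31/45 = 68.9% and 55/69 = 79.7%.
- Rates of 40% and 60%, centred on the roughly 50% the plan also mentions (cells 36/24/4/36): reported 60/64 = 93.8% and 36/40 = 90.0%; true with h = 10, 60/74 = 81.1% and 26/40 = 65.0%.

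**5. Positives (item 3), worst case.** Cells as in step 2, all positives real, no hidden cases, share c confirmed in every cell. True PPV and specificity are 100%. Reported PPV = 35c/35 = c. Reported specificity = TN/(TN + FP), with TN = 61 + 4(1 − c) and FP = 35(1 − c).

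| c (assumed) | Reported PPV | Reported specificity |
|---|---|---|
| 60% | 60% | 62.6/76.6 = 81.7% |
| 80% | 80% | 61.8/68.8 = 89.8% |
| 95% | 95% | 61.2/62.95 = 97.2% |

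**6. The double-positive conflict.** If all 11 double positives are unequivocal and count automatically, PPV becomes (11 + 24c)/35. At the same three shares this is 25.4/35 = 72.6%, 30.2/35 = 86.3% and 33.8/35 = 96.6%. The choice between the two sections alone moves PPV by 12.6, 6.3 or 1.6 points.

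**7. The paired comparison.** Based on scan positivity, the difference is 35 − 15 = 20 points whatever was verified. Based on confirmed metastasis it is 20c, or 12, 16 or 19 points. With all positives confirmed, the sensitivity ratio is [35/(39 + h)]/[15/(39 + h)] = 35/15 = 2.33, free of h.

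**The case against.** A reader might infer that the plan has no reference standard at all. It does: item 4 names one, and in a paired design a metastasis confirmed on one modality counts as a false negative for the other. The gap is complete only for men negative on every scan. For the rest, sensitivity is relative to the other scans performed. Nor is sensitivity 100% by construction, because the conventional-only cases supply false negatives.

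A reader might also infer that positives without tissue all default to false positive. They do not: section 5.1 provides post-treatment imaging as a second route. Item 3 therefore misclassifies only real positives for whom neither route was completed. Step 6 does not plainly cancel that route, since it says follow-up is not required; but steps 5 and 6 do not fit together as written.

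It is tempting to use the 41.4% in section 1.2.1 as a confirmation rate. It is the pathology share among true-positive scans in a retrospective series, where the others were confirmed by conventional imaging, so it is not used here.

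The direction of bias is not guaranteed. If real positives are confirmed less often than missed cases are proven, sensitivity is understated: with assumed true sensitivity of 80% among 50 diseased men, 60% of detected cases confirmed and every missed case proven, it is reported as 24/(24 + 10) = 70.6%. Item 4 also omits the imaging qualifier that section 5.1 attaches to treatment response, so responses not reflecting metastasis could lower NPV. The imaging reading is the better supported, but item 4 leaves the question open.

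Finally, the sample size rests on detection rate, and section 1.3 calls expanded access the key objective. Both are true, and the comparison is untouched if detection means scan positivity. Objective B and section 5.6 remain affected.

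**Conclusion.** The point stands in this form. The classification rules as written would misreport objective B's measures wherever verification is incomplete, and no passage verifies men negative on every scan. Sections 5.1 and 5.5 also contradict each other on unconfirmed double positives.

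Confidence is high on the missing class and the contradiction, and low on the size of any bias. The documents give neither the number of metastases missed by every scan nor the share of positives confirmed. With 10 unproven hidden cases, the three sets of cells tried overstate PET sensitivity by 12.7 to 19.7 points (93.8 − 81.1; 88.6 − 68.9) and NPV by 14.5 to 25.0 points (94.2 − 79.7; 90.0 − 65.0). The specificity and PPV losses assume every positive is real, which is a worst case, since section 6.2 warns of false positives.

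**What to change.** In section 5.5, with matching edits to section 5.1:

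1. Class image-negative patients who have no reference data beyond the scans under test as *unverified*, not true negative.
2. Class positives for whom neither pathology nor post-treatment imaging or response data were obtained as *unverified*, not false positive.
3. Report all four measures with lower and upper bounds over the unverified patients. Where all-negative men are unverified, describe sensitivity and NPV as relative to the scans performed.
4. Report paired relative true-positive and false-positive fractions among patients positive on either test, with the number verified in each cell and bounds for the rest.
5. Report item 4 results with and without false negatives that rest only on treatment response.
6. Reconcile the double-positive rule in section 5.1 with items 1 and 3, and reconcile steps 5 and 6 of section 5.1.
7. State whether the paired comparison uses scan positivity or confirmed metastasis.

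The cost is wording and extra tables from data already planned, with no new patients, procedures or follow-up. The price is width. In the main illustration with every positive confirmed, PET sensitivity runs from 35/100 = 35.0% to 35/39 = 89.7% and NPV from 0/65 = 0% to 61/65 = 93.8%; specificity is undefined (0/0) if all 61 negatives are set to diseased. The paired sensitivity ratio is more informative: with 80% of positives confirmed in each cell, it runs from (11 + 24 × 0.8)/15 = 2.01 to (11 × 0.8 + 24)/(15 × 0.8) = 2.73.

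These changes disclose the gap and limit what can be concluded. They do not supply a reference standard for men negative on every scan.

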2. STUDY OBJECTIVES

Based on these rationales, this clinical trial will address the following objectives:

- A. Provide expanded access the drug ^{11}C -choline.
- B. Determine the performance characteristics (sensitivity, specificity, positive predictive value, negative predictive value) of ^{11}C -choline PET/CT and PET/MRI in the detection of metastatic prostate cancer in patients with biochemical relapse of prostate cancer after primary treatment in a prospective manner.
- C. Determine the optimal PSA trigger value in ^{11}C -choline PET/CT and PET/MRI positive patients through a prospective study.
- D. Determine factors that predict a confirmed positive ^{11}C -choline PET/CT and PET/MRI using a multivariable analysis of clinical and pathologic data collected prospectively.
- E. Compare the individual performance characteristics of ^{11}C -choline PET/CT and ^{11}C -choline PET/MRI and the combination of ^{11}C -choline PET/CT and PET/MRI

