5.6 Publishing the Study Data

Upon completion of the clinical study, it is the intention of the Investigators and Study Sponsor to report the performance characteristics (sensitivity, specificity, positive predictive value, negative predictive value) of ^{11}C -choline PET/CT and PET/MRI in the detection of metastatic prostate cancer in patients with biochemical relapse of prostate cancer after primary treatment in a prospective manner and compare to the performance characteristics with those of conventional imaging. We will also report the performance characteristics of ^{11}C -choline PET/CT compared to ^{11}C -choline PET/MRI and the combination of ^{11}C -choline PET/CT and PET/MRI. Finally, we will report the demographic, clinical, and pathologic factors that predict a positive ^{11}C -choline PET/CT or PET/MRI in the two study groups.

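### Item 8 and section 5.6 model a positive scan where Objective D asks about a confirmed positive, and the PSA trigger (Objective C, item 7) has no stated outcome or criterion

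*Combined protocol and SAP*

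**What the plan says.** All references are to the main imaging protocol; the appended expanded-access protocol plans no data analysis.

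- Section 2, Objective D: "Determine factors that predict a confirmed positive ^{11}C -choline PET/CT and PET/MRI using a multivariable analysis".
- Section 5.5, Data Analysis item 8: "Demographic, clinical, and pathologic factors that predict a positive ^{11}C -choline PET/CT or PET/MRI will be determined through a multivariable analysis". Section 5.6 promises a report on "pathologic factors that predict a positive ^{11}C -choline PET/CT or PET/MRI in the two study groups". Neither mentions confirmation.
- Section 5.5 item 1 makes a positive scan true if it is confirmed by biopsy, surgical pathology "or by response to treatment with androgen suppression or other medical or radiation therapy". Item 3 makes it false if it shows metastasis "but without corresponding confirmation from biopsy, surgical pathology or response to treatment".
- Section 2, Objective C: "Determine the optimal PSA trigger value in ^{11}C -choline PET/CT and PET/MRI positive patients through a prospective study". Item 7: "The optimal PSA trigger value in ^{11}C -choline PET/CT and PET/MRI positive patients will be calculated". Neither names what the trigger should separate or how the optimum is defined.
- Section 1.2.1 describes an earlier study of 190 patients that compared PSA in PET-positive and PET-negative men and took a cut-off of 2.43 ng/mL from a ROC analysis. That is background, not this trial's method.

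**The concern.** The plan itself treats a confirmed positive and a positive as different things, since items 1 and 3 exist to separate them. A model built on item 8 therefore counts as events some scans that item 3 calls false, and none of items 1 to 8 models the outcome in Objective D. This bears most on PSA: section 6.2 links values below 2 ng/mL to more false positives, so PSA is a factor whose association could differ between the two outcomes.

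For the trigger, every patient in a scan-positive set has the same scan result, so PSA cannot be tuned there to predict that result. With outcome, patient set and criterion unsettled, a favourable combination could be picked once the data are known.

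**Working it through.** **The plan's own figure.** Objectives C and D have no figure to reproduce. The only sample-size result, 66 pairs, concerns the paired detection-rate comparison. With discordant cells 0.20 and 0.04, two-sided 0.05 and 80% power: (1.960 + 0.842)² × (0.24 − 0.16²)/0.16² = 65.73, so 66. It reproduces and does not bear on this point.

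**Inputs from the documents.** Positive scans per 100: 35 (the goal in section 5.5) or 50 (its literature detection rate). From the retrospective series of 176 patients in section 1.2.1: sensitivity 93%, specificity 76%, PPV 91%. From section 5.5: "It was further assumed that the false positive rate is about 4 % and the false negative rate is about 20" per cent.

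**Assumed.** Patients split 50/50 at PSA 2 ng/mL. True odds ratio (high v low PSA) for a true positive: 3. False positives split evenly, or two-thirds below 2 ng/mL (direction from section 6.2, share assumed).

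**Step 1: PPV.** It depends on prevalence π. With 0.93π + 0.24(1 − π) = proportion positive, π = (proportion − 0.24)/0.69.
- 50 positives: π = 0.26/0.69 = 0.377; true positives 35.04, false 14.96; PPV 70%.
- 35 positives: π = 0.11/0.69 = 0.159; true positives 14.83, false 20.17; PPV 42%.
- PPV 91% with the same sensitivity and specificity needs π of about 72% and 74 positives per 100.

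**Step 2: any-positive odds ratio.** Solve [a/(50 − a)]/[b/(50 − b)] = 3 with a + b = true positives, add the false positives to each half, and recompute.

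| Positives | PPV | a / b | Even split | Two-thirds low |
|---|---|---|---|---|
| 35 | 91% | 21.68 / 10.17 | 2.83 | 2.56 |
| 50 | 91% | 29.39 / 16.11 | 2.97 | 2.61 |
| 50 | 70% | 23.58 / 11.46 | 2.69 | 1.78 |
| 35 | 42% | 10.68 / 4.15 | 1.78 | 0.98 |

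Example, last cell: high half 10.68 + 6.72 = 17.40, low half 4.15 + 13.45 = 17.60; (17.40/32.60)/(17.60/32.40) = 0.98. If the plan's 4% is read as 4 false positives per 100 imaged, the range is 2.46–2.98.

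**Step 3: the confirmed outcome when confirmation is incomplete.** Confirmed events are a × v(high) and b × v(low), with verification shares v assumed. At PPV 91%, over 35 and 50 positives:

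| v high / v low | Unconfirmed as non-events | Unconfirmed excluded |
|---|---|---|
| 80% / 80% | 2.56–2.73 | 2.95–3.14 |
| 90% / 70% | 3.86 | 3.79–4.04 |
| 70% / 90% | 1.71–1.95 | 2.29–2.45 |

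At 80%/80% and the lower PPVs, the non-event run gives 2.70 (50 positives, PPV 70%) and 2.90 (35, PPV 42%). Exclusion gives 2.74–3.37 and 2.56–3.15.

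**Step 4: events per 100 with full verification.** At PPV 91%: 35 × 0.91 = 31.9 and 50 × 0.91 = 45.5. At PPV 70% with 50 positives: 35.0. At PPV 42% with 35: 14.8.

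**The case against.** **Shorthand.** Section 5.1 item 5 says that imaging evidence of metastasis is to be confirmed, so item 8 may simply have left the word out. That is possible, but item 3 provides for positives that stay unconfirmed, and section 5.6 repeats the omission. The text still has to say which outcome is meant.

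**The remedy may be no better.** At PPV 91%, the any-positive model (2.6–3.0) is as close to 3 as the confirmed model with unconfirmed scans as non-events (2.6–2.7 at uniform 80% verification), and closer than that model when verification depends on PSA (1.7–3.9). This stands, and it is why no single handling should be reported alone. At the lower PPVs with uniform verification the order reverses: 2.7–2.9 for the confirmed model against 1.0–2.7. Rewriting Objective D to match item 8 would also remove the mismatch, but it would give up the question the protocol set.

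**Objective C can be computed.** A reader might infer that no trigger can be derived from scan-positive patients. The documents do not support that: a cut-off between confirmed and unconfirmed positives is computable. The plan does not say it is intended.

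**Secondary matter.** Neither analysis is the powered comparison, and section 1.3 gives expanded access as the main aim. Both facts stand and limit the weight of the point. They do not leave Objectives C and D answered.

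**Conclusion.** The point holds as one of alignment and pre-specification. Objective D has no matching analysis. Objective C and item 7 name a patient set in which the usual trigger contrast does not exist, and give neither outcome nor criterion.

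The size is not fixed by the documents. Against an assumed true odds ratio of 3, the any-positive value is 2.6–3.0 at PPV 91%, 1.8–2.7 at PPV 70% and 1.0–1.8 at PPV 42%, given the even PSA split and the assumed placement of false positives. A reader might infer from the cited 91% that the distortion must be small. That does not follow, because the sensitivity and specificity reported with it imply 91% only at about 72% prevalence. Nor is a large distortion shown, since this trial's prevalence and specificity are unknown.

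Two other readings go too far. The mismatch does not undermine the 66-pair calculation or the detection-rate comparison. And the confirmed outcome is not unbiased by construction: it is open to verification bias whenever confirmation depends on PSA.

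**What to change.** (a) Reword item 8 and section 5.6 so that the outcome is a confirmed positive, as in Objective D. Report three runs side by side: unconfirmed positives excluded, unconfirmed positives as non-events, and any positive. State that exclusion nearly removes the bias only if verification does not depend on PSA (and less fully at a low PPV), and that otherwise none of the runs removes it.

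(b) Reword Objective C and item 7 as a ROC analysis in all imaged patients, positive and negative, for PET/CT and for PET/MRI, with outcome and optimality criterion fixed in advance. One example is the PSA value that maximises sensitivity plus specificity for a positive scan, with an interval. Another pre-stated criterion would also close the gap.

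(c) Reconcile the passages on which confirmation depends. Section 5.1 item 5 accepts unequivocal findings on both conventional imaging and PET as a true positive, while section 5.5 item 1 requires pathology or treatment response. Section 5.1 item 5 also relies on imaging three months after treatment ends, while item 6 releases the patient without further follow-up once results are sent.

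**Cost.** Parts (a) and (b) are wording and analysis time. The confirmed outcome has fewer events, hence wider intervals, and a cut-off from 100 patients will be imprecise. Possible verification bias remains. Until (c) is settled, the confirmed outcome rests on data the plan does not secure; if the off-study rule governs, obtaining them would be additional work.
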